MitoQ for Fatigue in Multiple
Sclerosis: A Placebo Controlled Trial

NCT04267926

September 23, 2021

Title

MitoQ for fatigue in multiple sclerosis: a placebo-controlled trial

Specific Aims/Purpose

Specific Aim 1: Determine whether Veteran's with MS (VwMS) who receive oral MitoQ in comparison to those who receive placebo have less fatigue after a 12-week treatment period as measured by MFIS Score.

Specific Aim 2: Determine whether VwMS who receive oral MitoQ in comparison to those who receive placebo have improved cognitive function, quality of life and depression using Symbol Digit Modality Test (SDMT), MS Impact Scale -29 (MSIS-29) and the Beck Depression Inventory–Fast Screen scores respectively.

Specific Aim 3: Determine the safety and tolerability of MitoQ in VwMS using side effects and blood tests.

Specific Aim 4: Determine whether plasma MitoQ levels in VwMS treated with MitoQ correlate with clinical outcomes of fatigue, cognitive function, quality of life and depression and with blood based inflammatory immune and oxidative stress biomarkers.

The proposed work is innovative; the

Hypothesis: The central hypothesis is that oral MitoQ with its mitochondrial affinity will improve MS related fatigue, cognition, quality of life and mood by improving mitochondrial function and resultant neuronal energy depletion in neurons.

Research Design and Methods

We propose to conduct a double-blind, placebo-controlled, pilot trial to compare the administration of a 20 and 40 mg dose of oral MitoQ to a placebo, as a treatment to reduce fatigue in MS subjects. There is no research to guide the study supplement dosage for this study. We have chosen 20 and 40 mg dosages based on correspondence from the manufacturer as noted above, in addition to the published recommendation in an article reviewing all the human and animal studies on MitoQ. The participation period for each subject will be 13 weeks: screening visit during the first week, followed by a 12-week treatment period. The study will require 4 visits and 4 phone calls over 13 weeks. Total time commitment is approximately 7 hours.

Overall Design

Aims	Outcomes	Description

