Anticipated results: We expect that MS veterans taking MitoQ will have better cognition and quality of life and less depression than those Veterans with MS taking placebo as determined by the standard measures.

Specific Aim 3: Determine the safety and tolerability of MitoQ in subjects with MS using side effects and blood tests.

Introduction: Results from clinical trials in Hepatitis C and PD as described in the “current status of the field section” suggested that MitoQ is generally well-tolerated and no safety concerns surfaced. To assess the safety and tolerability of oral MitoQ versus a placebo, all subjects (treatment as well as the placebo groups) will undergo monitoring for AEs and side-effects as described below. An adverse event is any untoward medical occurrence (signs, symptoms, intercurrent illness or abnormal lab findings) that occurs in a study subject during the treatment or cross over periods, regardless of suspected cause.

Statistical Analysis: To evaluate patient safety, laboratory test results at baseline and changes from baseline at 6 and 12 weeks will be determined and summarized for each subject group, and will be compared using t-tests for continuous measures and Fisher’s exact test for proportions.

Anticipated results: We expect that MS veterans taking MitoQ will have no significant and unexpected AE on their blood tests and body systems than those Veterans with MS taking placebo.

Specific Aim 4: Determine whether plasma MitoQ levels in Veterans with MS treated with MitoQ correlate with clinical outcomes of fatigue, cognitive function, quality of life, depression, blood inflammatory immune markers, and markers of oxidative stress. We will test the hypothesis that plasma concentrations of MitoQ correlate with fatigue, cognitive function, quality of life and depression in subjects with MS receiving MitoQ compared with those receiving placebo. Additionally, this aim will test the hypothesis that MitoQ will lower the blood concentration of inflammatory immune markers and markers of oxidative stress. We hypothesize that MS subjects receiving MitoQ will have improved levels of blood biomarkers of oxidative stress as seen by lower lipid peroxidation (LPO) products, nitric oxide catabolites (NOC) and superoxide dismutase (SOD) activity and improved TAC.

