Introduction: Pharmacokinetic (PK) studies of oral MitoQ have been conducted in healthy human subjects but not in MS. Healthy human PK studies suggest maximal plasma concentration (Cmax) of MitoQ after oral dosing at 40 mg (0.5 mg/kg) and 20 mg (0.25 mg/kg) to have detectable and maximal concentration ~1hr. Limited CoQ10 studies in MS suggest significant impact on cytokine and oxidative stress biomarker profile hence we believe that MitoQ may have similar effects too. We now have good in vitro data on the ability of MitoQ to suppress LPS-induced cytokine production in human peripheral blood mononuclear cells and this study will provide a novel opportunity to explore the biologic effects of MitoQ. With the data collected on clinical outcomes such as fatigue, cognition, depression and QOL in this study, we will be able to generate pilot data correlating the PK, immune markers and these clinical outcomes.

Statistical analysis. We will construct Q-Q plots on all data to test for normalcy. Using Pearson correlations for parametric data or Spearman Rho correlations for nonparametric data, we will determine linear associations among changes in cytokines including IFN- γ , TNF- α , and IL-2 and plasma levels of MitoQ. We will use repeated measures mixed effects models to investigate the linear relationships between pro-inflammatory markers, oxidative stress biomarkers, cytokines, and MitoQ levels over time (i.e., at 6 and 12 weeks). We will examine correlation between measures of oxidative stress as well as the correlation between oxidative stress markers and plasma levels of MitoQ. We will obtain mean changes from baseline to 12 weeks and 95% confidence intervals for the oxidative stress markers. The correlations, means, and standard deviations observed in the oxidative stress biomarkers of this study will help inform power and sample size calculations in future trials. Statistical significance is defined as $P < 0.05$.

Anticipated results: We expect that plasma concentrations of MitoQ will correlate with fatigue, cognitive function, quality of life and depression in subjects with MS and that subjects receiving MitoQ will have lower blood concentration of inflammatory and oxidative stress markers.

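### Does Aim 4's correlation of plasma MitoQ level with clinical outcomes need a rewritten hypothesis and a fuller analysis section?

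*Combined protocol and SAP*

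**What the plan says.** In the combined protocol and SAP, the Specific Aims list gives Aim 4 as: "Determine whether plasma MitoQ levels in VwMS treated with MitoQ correlate with clinical outcomes of fatigue". The opening of the Specific Aim 4 section repeats it: "Determine whether plasma MitoQ levels in Veterans with MS treated with MitoQ correlate with clinical outcomes of fatigue". The Aim 4 row of the Overall Design table names the same population. Six targets are named: fatigue, cognitive function, quality of life, depression, inflammatory immune markers and oxidative stress markers.

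The hypothesis that follows in the Specific Aim 4 section adds a contrast for the four clinical targets: "quality of life and depression in subjects with MS receiving MitoQ compared with those receiving placebo".

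The Aim 4 Introduction says that "we will be able to generate pilot data correlating the PK, immune markers and these clinical outcomes". The Aim 4 Statistical analysis opens with Q-Q plots on all data. It then says "Using Pearson correlations for parametric data or Spearman Rho correlations for nonparametric data", "we will determine linear associations among changes in cytokines including" three named examples, and plasma MitoQ. It adds repeated-measures mixed models for "the linear relationships between pro-inflammatory markers, oxidative stress biomarkers, cytokines, and MitoQ levels over time", at 6 and 12 weeks, and "the correlation between oxidative stress markers and plasma levels of MitoQ". No clinical scale is named there. The Anticipated results restate the clinical correlation and attach no placebo comparison to it.

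**The concern.** There are two apparent faults. First, a correlation with drug level needs levels that vary. If placebo patients have none, the contrast in the hypothesis has no placebo counterpart, and it also departs from the population that the aim defines. Someone who took the clause as an instruction to pool the arms could mistake a plain treatment effect for a concentration-response.

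Second, the hypothesis is said to be tested and the section sets P < 0.05. Yet none of MFIS, FSS, SDMT, MSIS-29 and BDI-FS appears under the level-based methods. The nearest analyses, in the Aim 1 Data Analysis, use assigned dose (the ANOVA trend on MFIS) or pill count (for FSS). Choices such as the scale of the level and adjustment for dose would then be open after the data are seen.

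**Working it through.** The document gives no sample size, effect size or level distribution for this aim, so there is no figure of its own to reproduce. The check is a count, a comparison of the sections, and one illustration with assumed inputs.

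**Count of targets against listed level-based analyses**

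| Aim 4 target | Listed analysis against plasma level |
|---|---|
| Fatigue (MFIS, FSS) | none |
| Cognitive function (SDMT) | none |
| Quality of life (MSIS-29) | none |
| Depression (BDI-FS) | none |
| Inflammatory immune markers | Pearson/Spearman; mixed model |
| Oxidative stress markers | correlation; mixed model |

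So 6 − 2 = 4 targets, covering five scales, have no listed analysis against level. They do have between-arm analyses under Aims 1 and 2.

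**Population.** Three statements of the aim (Specific Aims list, Overall Design table, Specific Aim 4 opening) restrict the correlation to patients treated with MitoQ. The Anticipated results carry no placebo contrast for it. One clause in the hypothesis departs from this.

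**Placebo arm.** r = cov(X, Y) / (SD(X) × SD(Y)). With X = 0 for every placebo patient, SD(X) = 0 and r is undefined. This rests on the assumed zero level.

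**What pooling would do, if anyone did it.** Assume three equal arms, placebo level 0, log-normal levels with medians 1 and 2 and log-SD 0.4 in the MitoQ arms, no relation of level to outcome within any arm, and the same effect of d SD at both doses.

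- Mean level in treated patients = 1.5 × exp(0.08) = 1.625, so the overall mean = (2/3) × 1.625 = 1.083.
- Mean square of level = (1/3) × (1 + 4) × exp(0.32) = 2.295, so the variance = 2.295 − 1.083² = 1.122 and the SD = 1.059.
- Covariance = d × (2/3) × (1/3) × 1.625 = 0.361d; outcome variance = 1 + (2/9)d².
- Pooled r = 0.361d / (1.059 × √(1 + (2/9)d²)) = 0.10, 0.17 and 0.26 for d = 0.3, 0.5 and 0.8.

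Simulation gave 0.10, 0.16 and 0.26, against 0.00 in the treated arms alone. Pooling would therefore mislead, but the plan does not call for it and the aim's stated population rules it out.

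**Dose adjustment within the treated arms.** These simulations assumed 10 to 30 patients per arm, arm effects of 0.5 to 0.8 SD, log-SD 0.5, median levels 1:2 and no concentration-response within an arm.

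- A mixed model with dose group gives P < 0.05 in 5–6% of trials. Without dose group it gives 5–6% if both doses have the same effect, and 7–18% if the 20 mg effect is half the 40 mg effect.
- Adding dose removes the randomised part of exposure: (ln2/2)² / ((ln2/2)² + 0.5²) = 0.120 / 0.370, about 32% of log-level variance.
- Adding dose also widens the 95% CI half-width for the slope per doubling of level from about 0.33 to 0.40 outcome SD with 20 treated patients, and from 0.18 to 0.21 with 60.

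Neither choice is plainly better.

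**The case for a change.** The strongest case for a change is that a declared hypothesis with a significance threshold should have a declared analysis, and a sentence of intent in an Introduction is not one. The Aim 1 statement that secondary outcomes are handled in the same way does not help, because those models compare arms and never use plasma level. Two doses, two post-baseline visits and five scales leave room for selection. Table 2 schedules level draws without distinguishing arms, so placebo values may exist in the dataset. The remedy looks cheap, since level and most of the scales are already collected at the same visits.

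The count stands, and so does the looseness of the clause. The rest is weaker. The population is fixed by the aim itself. The time points and the normality rule are in the section, written for the markers and readily carried over. What remains open, the scale of the level and adjustment for dose, is equally open for the marker analyses, so it does not mark out the clinical correlations. A full specification would have to settle the dose question, add baseline and random participant terms that the Aim 4 model does not state, and supply a rule for values below the assay limit. Those are matters of preference in an exploratory analysis. Listing more fits would not make the P-values safer either: with no true association, ten fits (five scales, with and without dose) give at least one P < 0.05 in about 24–34% of trials, by single-visit regression with outcome correlations of 0.6 down to 0.

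**Conclusion.** No change is needed. The placebo clause is a drafting slip: it probably borrows the between-arm contrast that belongs to Aims 1 and 2, or to the biomarker hypothesis in the next sentence. The three statements of the aim and the Anticipated results already correct it. The missing scale names are a gap that a competent analyst would fill by applying the section's own correlation and mixed-model methods to the five scales in the treated arms, and by reading the results as pilot estimates.

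The only size that comes from the document is the count, 4 of 6 targets. The pooling figures need an analysis that the plan does not contain, together with assumed effects and level distributions, so they carry no weight here. That the placebo correlation cannot be estimated also rests on an assumption, that placebo levels are zero or undetectable. The primary MFIS comparison and the Aim 2 comparisons do not depend on any of this.

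The differing BDI schedules (Overall Design table against Table 2 and the Aim 2 Procedures) are a separate matter to be reconciled on their own.

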1. Determine whether Veterans with MS who receive oral MitoQ in comparison to those who receive placebo have less fatigue after a 12-week treatment period as measured by MFIS Score.	Primary Outcome: MFIS Secondary Outcome: FSS	Double-Blind, randomized groups assigned to either 20 or 40 mg of MitoQ or an identical placebo. Check MFIS, and FSS and SDMT at time 0, 6 and 12 wks
2. Determine whether Veterans with MS who receive oral MitoQ in comparison to those who receive placebo, have improved cognitive function, quality of life and depression using SDMT, MSIS-29 and the BDI–FS scores respectively.	Secondary Outcome: SA-EDSS and BDI.	Double-Blind, randomized groups assigned to either 20 or 40 mg of MitoQ or an identical placebo. Check SA-EDSS and BDI at time 0 and 12 weeks
3. Determine the safety and tolerability of MitoQ in subjects with MS using side effects and blood tests.	Secondary Outcome: Safety.	Monitoring of patient response and reporting/recording AEs
4. Determine whether plasma MitoQ levels in Veterans with MS treated with MitoQ correlate with clinical outcomes of fatigue, cognitive function, quality of life, depression, blood inflammatory immune markers, and markers of oxidative stress.	Secondary Outcome: Plasma levels of oral MitoQ 1 hr post-drug. Plasma and/or PBMC IFN- γ , TNF- α , IL-2, IL-6 and IL-17, MDA, HAE, TAC, NOC and SOD	Data collection on MitoQ plasma levels and inflammatory and oxidative stress markers at baseline, week 6 and 12.

Subject Visits and Assessment Schedule

Table 2. Study Activities

	Week 0	Week 1	Week 7	Week 13	
	Visit 1	Visit 2	Visit 3	Visit 4	
Visit time	2 hours	2.5 hours	2.5 hours	2.5 hours	
Purpose	screen, consent	begin treatment	in clinic follow up	end treatment	Total blood draw amount
Consent	X				
Vital signs	X	X	X	X	
Medical history, physical neurological exam	X			X	
T25W, 9HPT, SDMT		X	X	X	
BDI, FSS, MFIS, MSIS-29	X	X	X	X	
Blood testing CBC w/ diff (4mls) CMP (6mls)	X		X	X	30 mls
Blood draw for plasma MitoQ level (4mls)		X	X	X	12 mls
Blood draw for Inflammatory immune markers 40 mls		X	X	X	120 mls
Medication reconciliation	X	X	X	X	
Urine testing (female)	X		X	X	
Side effect monitoring			X	X	

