Data Analysis: We will obtain descriptive information on primary and secondary outcomes. In particular, at each time-point, we will obtain the mean, median, SD, and range for each measure and for the changes from baseline for each measure, for the MitoQ and placebo subject groups. We will also obtain 95% confidence intervals for the changes from baseline for each measure, at each time point for both subject groups. We will conduct a t-test to compare primary and secondary measures (changes from baseline) and to obtain the associated 95% confidence intervals for the differences in mean change between the MitoQ and placebo subject groups. We will focus on the confidence intervals that describe the plausible differences in mean change between the subject groups. These confidence intervals will provide information about the magnitude of differences in MFIS and FSS changes between subject groups that are consistent with the previous data. We will also test for differences in the change scores by group in a linear regression framework, adjusting for demographic and clinical characteristics, such as gender. As a secondary analysis, we will use an ANCOVA test with 12-week MFIS score as the outcome and baseline MFIS score as a covariate to account for baseline differences in fatigue among patients. We will use a linear mixed model to analyze MFIS changes over time with fixed effects for time, incorporating baseline values of the outcome as a covariate, and random intercepts and slopes for individuals to incorporate within-subject variability. Due to the exploratory nature of this study, the 6 week time point will provide evidence of whether or not change is seen by 6 weeks. It will allow us to understand how long MitoQ takes to have an effect, and this information will be useful for planning future studies. Both formal hypothesis testing and confidence interval estimation will be conducted. To detect a trend in the effect of MitoQ dosage, we will perform an ANOVA trend analysis on the change in MFIS between baseline and 12 weeks among the three treatment groups. In addition, we will categorize participants who improved by a reliable change, defined as differences in group means divided by the standard error, greater than 1.96 points and test for differences in the proportion of improvers by group using a chi-squared test. The standard error is given by $s_1\sqrt{1 - r_{xx}}$, where s_1 is the standard deviation of the control group and r_{xx} is the MFIS test-retest reliability (here, given by the MFIS Cronbach's alpha value of 0.81.⁶ This analysis will yield additional power (compared to a 2-sample t-test) and will provide useful data for planning a repeated measures analysis in a future larger trial. Secondary outcomes will be analyzed in the same manner. To test if the effect of MitoQ on FSS depended on compliance, compliance (as measured by pill counting) will be treated as a co-variate in the analyses. Patterns of missing data will be examined to determine if patient characteristics are related to missing follow-up data. Statistical significance is defined as $P < 0.05$. SPSS for Windows Version 15.0 (SPSS Inc., Chicago) and SAS (SAS Institute, Cary, NC) will be used for analysis.

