
Anticipated results: We expect that MS veterans taking MitoQ for 12 weeks will have less fatigue than those Veterans with MS taking placebo as determined by the MFIS.

Specific Aim 2: Determine whether Veterans with MS who receive oral MitoQ in comparison to those who receive placebo have improved cognitive function, quality of life and depression using Symbol Digit Modality Test (SDMT), MS Impact Scale -29 (MSIS-29) and the Beck Depression Inventory–Fast Screen scores respectively. Our hypothesis is that by improving mitochondrial function in sub optimally functioning neurons and axons, MitoQ, an efficient mitochondrial targeted therapy, may lead to cognition, quality of life and depression improvement in Veterans with MS.

Introduction: In addition to fatigue, cognitive impairment, poor quality of life and depression are some aspects of MS that have significant adverse impact on patient's lives and not addressed by current treatment options including the disease modifying therapies. Mitochondrial targeted therapy CoQ10 has shown significant improvement in depression (BDI) and quality of life in a small pilot study as compared to placebo.⁴⁶ Since MitoQ is considered to have better mitochondrial penetration than CoQ10, it is worthy of exploring its effects on these poorly managed MS symptoms.

Procedures: At baseline assessment and visits 3 and 4 (6 and 12-week post treatment initiation assessment). At each of these visits, we will also acquire data on each subject's cognitive function using SDMT, quality of life assessment using MSIS-29 and depression using BDI-FS scores.

Statistical Analysis: Exploratory analyses similar to the primary analysis including mixed model that will account for repeated measures will be conducted using the SDMT, MSIS-29 and BDI-FS as the secondary outcome measures. To test if the effect of MitoQ depended on changes in depression a similar model will be constructed including both the baseline and the end of the period BDI-FS. The effect of MitoQ on depression will be evaluated by fitting a model with BDI-FS at the end of each period as the outcome. Baseline values for the SDMT, MSIS-

29, BDI-FS and FSS will be included as covariates, and patient effects treated as random. Changes in activity over time will be analyzed in an exploratory manner using graphical techniques.

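### The Aim 4 mixed models state no baseline marker term, although baseline markers are collected; adding one would sharpen the level-marker slope and reduce, but not remove, possible confounding

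*Combined protocol and SAP*

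**What the plan says.** Specific Aim 4, Statistical analysis, plans repeated-measures mixed models for the inflammatory markers together with "oxidative stress biomarkers, cytokines, and MitoQ levels over time (i.e., at 6 and 12 weeks"). It names no covariates, random effects or outcome scale for these models.

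Baseline values will exist. The Aim 4 row of the Overall Design table gives "Data collection on MitoQ plasma levels and inflammatory and oxidative stress markers at baseline, week 6 and 12", and Table 2 places the inflammatory marker draw at Visits 2, 3 and 4.

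Baseline is handled explicitly in other places:
- **Aim 1 mixed model for MFIS:** "incorporating baseline values of the outcome as a covariate, and random intercepts and slopes for individuals".
- **Aim 2 models:** the list of baseline values starts with SDMT and MSIS-29 and ends "29, BDI-FS and FSS will be included as covariates, and patient effects treated as random" (the leading 29 belongs to MSIS-29).
- **Aim 4 cytokine correlations:** "we will determine linear associations among changes in cytokines including" three named cytokines and plasma MitoQ level.
- **Aim 4 oxidative stress markers:** "We will obtain mean changes from baseline to 12 weeks and 95% confidence intervals for the oxidative stress markers". This is descriptive and does not involve drug level. The separate correlation of these markers with plasma level is not specified as a change.

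**The concern.** Patients differ in their usual marker values for reasons unrelated to treatment. A model of week 6 and week 12 values with no baseline term leaves that stable variation in the residual and widens the interval for the level-marker slope. Aim 4 is meant to supply means, standard deviations and correlations for planning later trials, so lost precision matters there.

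There is also a possible bias. Dose is randomised, but the plasma level reached within a dose arm is not. If some patient characteristic affects both the level and the usual marker value, the two will be associated even when MitoQ does nothing. A negative association of that kind would look like the drug lowering the marker, which is the Aim 4 hypothesis.

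For cytokines, the planned correlations of changes partly guard against both problems. For oxidative stress markers, no stated analysis against drug level uses baseline.

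**Working it through.** The plan gives no sample size, marker variance or marker reliability for Aim 4, so there is no figure to reproduce. The inputs below are assumptions.

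**Precision.** Let the marker have variance 1 and correlation *r* between any two visits. Let plasma level have variance 1, with a share *w* between patients and 1 - *w* within patients, unrelated to the baseline marker. For two follow-up visits, the information on the slope per patient is the sum of a between-patient and a within-patient part:

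- without baseline: (1 + w)/(1 + r) + (1 - w)/(1 - r)
- with baseline covariate: (1 + w)/(1 + r - 2r²) + (1 - w)/(1 - r)

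The standard error ratio (with / without) is the square root of the first divided by the second. The small loss of degrees of freedom is ignored.

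| w | r | Without baseline | With baseline | SE ratio | Reduction |
|---|---|---|---|---|---|
| 1 | 0.5 | 2/1.5 = 1.333 | 2/1.0 = 2.000 | √0.667 = 0.816 | 18% |
| 1 | 0.7 | 2/1.7 = 1.176 | 2/0.72 = 2.778 | √0.424 = 0.651 | 35% |
| 0.5 | 0.5 | 1.5/1.5 + 0.5/0.5 = 2.000 | 1.5/1.0 + 0.5/0.5 = 2.500 | √0.800 = 0.894 | 11% |
| 0.5 | 0.7 | 1.5/1.7 + 0.5/0.3 = 2.549 | 1.5/0.72 + 0.5/0.3 = 3.750 | √0.680 = 0.824 | 18% |

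In patient numbers, the gain is worth a factor of 1.5 to 2.4 when level is constant within patient (2.000/1.333 and 2.778/1.176). It is worth 1.25 to 1.47 when half the level variance is within patient (2.500/2.000 and 3.750/2.549).

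**Spurious slope.** Suppose there is no drug effect, level is constant within patient, and level has correlation ρ with the patient's stable marker component. The expected slopes are:

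- follow-up values only: ρ√r
- with baseline covariate: ρ√r(1 - r)/(1 - rρ²)
- change from baseline: 0

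For r = 0.7 and ρ = 0.3 these are 0.3 × 0.837 = 0.251; 0.251 × 0.3/0.937 = 0.080; and 0. A negative ρ gives the same sizes with a negative sign.

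A simulation of this setting (5,000 data sets, 40 treated patients assumed, two-sided 0.05) rejected in 40%, 13% and 5% of data sets respectively. At ρ = 0 all three were at 5%.

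A fitted random-intercept model with level varying between visits (300 data sets, r = 0.7, ρ = 0.5) rejected in 53% without baseline and 19% with it. So a random patient effect does not remove the problem, and a single baseline covariate reduces it only in part, because one value measures the stable component with error. The change score is clean here because the stable component was assumed to act equally at every visit.

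These rates show the mechanism. They are not estimates for this trial.

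**The case against.** **The plan is silent; it does not exclude baseline.** A reader might infer that the plan deliberately drops the baseline value. The text does not support that. Naming weeks 6 and 12 is compatible with follow-up outcomes plus a baseline covariate. The Aim 1 analysis section also says that secondary outcomes get the same treatment as the primary, and the design table lists the Aim 4 measures as secondary outcomes. That sentence sits under Aim 1 and may or may not reach Aim 4. What remains is that the Aim 4 models state no baseline term and Aim 4 has no cross-reference that supplies one.

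**Aim 4 already uses baseline in part.** This stands for cytokines, through the correlations of changes, and it narrows the gap mainly to oxidative stress markers.

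**The larger precision gain is a best case.** This also stands. The 18-35% needs a level that is constant within patient, whereas levels are single draws about one hour after dosing.

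**The bias cannot be sized.** A reader might take the dose conversion "after oral dosing at 40 mg (0.5 mg/kg) and 20 mg (0.25 mg/kg"), which implies 80 kg (40/0.5 and 20/0.25), and infer that heavier patients have lower levels and higher markers, with a calculable false-positive rate. The documents do not support that step. The conversion comes from healthy-subject pharmacokinetics. No weight distribution, weight-level relation, weight-marker relation or sample size is given, and markers may be measured in plasma and/or PBMC.

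**Placebo patients would dilute it.** The Aim 4 text refers both to patients treated with MitoQ and to a comparison with placebo, so the model population is unclear. In one illustrative simulation without baseline, with 40 treated patients and assumed weight-marker correlations of 0.3, 0.4 and 0.5, adding 20 placebo patients lowered the false-positive rate from 11, 15 and 22% to 8, 9 and 13%. The bias was smaller but still present.

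**Conclusion.** The point holds as a modest, nearly free improvement. The Aim 4 mixed models state no baseline marker term even though the value is collected and the models for Aims 1 and 2 name baseline covariates.

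The firmer consequence is lost precision: a standard error reduction forgone of about 11-18% or 18-35%, depending on how stable plasma level is within a patient. Both ranges rest on assumed marker correlations of 0.5 to 0.7.

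A spurious level-marker slope is possible, but it requires a real link between level and usual marker value. The documents neither establish that link nor allow it to be sized. If level and usual marker value are unrelated, the false-positive rate stays near 5% and only precision is lost.

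Aim 4 is secondary and exploratory. What is affected is how its exposure-response findings are read and carried into later trials.

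**What to change.** In Specific Aim 4, Statistical analysis:

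1. State that each mixed model has the week 6 and week 12 marker values as outcomes and that marker's baseline value as a covariate.
2. Define baseline as the Visit 2 sample drawn before the first dose. Table 2 makes Visit 2 both the start of treatment and a plasma-level draw, and levels are described as taken one hour after dosing, so the order of sampling needs to be written down.
3. Define the correlations of oxidative stress markers with MitoQ level on change from baseline, as is done for cytokines.
4. Report a change-from-baseline version of each mixed model as a sensitivity analysis, because the covariate alone may leave residual confounding.

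The cost is one degree of freedom per model, a few lines of text and a little more analysis. No additional visits or blood draws are needed. Fixing this in advance also avoids a choice between adjusted and unadjusted models after the data are seen.
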